14.2 Clinical Laboratory Variables

Clinical chemistry serum tests include the following:

- Sodium (Na), potassium (K), chloride (Cl), phosphorus (P), calcium (Ca), carbon dioxide (CO₂), blood urea nitrogen (BUN), creatinine (CR), uric acid

- Alanine aminotransferase (ALT), aspartate aminotransferase (AST), gamma-glutamyl transpeptidase (GGT), alkaline phosphatase (ALP), total bilirubin (TBIL), lactate dehydrogenase (LDH)
- Magnesium (Mg) should only be performed at Visit 1 (Screening)
- Vitamin B12 should only be performed at Visit 1 (Screening)
- HbA1c should only be performed at Visit 1 (Screening), Visit 6, and Visit 17/ET
- Glucose
- Albumin (ALB), total protein
- Prolactin
- Thyroid stimulating hormone (TSH) and free T4
 - TSH should be performed only at Visit 1 (Screening)
 - Free T4 will be measured only if TSH is abnormal
- Lipid Panel
 - Total cholesterol, high-density lipoprotein (HDL)-cholesterol, triglycerides, low-density lipoprotein(LDL)-cholesterol, cholesterol/HDL ratio, non-HDL cholesterol

Hematology tests include the following:

- Complete blood count (CBC) including:
 - White blood cell (WBC) count
 - Complete differential (relative and absolute)
 - Hematocrit (Hct), hemoglobin, red blood cells (RBC), platelets
 - Reticulocyte count

Urinalysis tests include the following:

- Color, clarity, blood, RBCs, WBCs, protein, glucose, ketones, specific gravity, pH, leukocyte esterase, nitrite, microscopic analysis

All laboratory test results (including urine drug screen) are from a central laboratory and will be listed. The listings will include date and study day of collection. All units will be displayed

in Système International [SI] units. Out of range values will be flagged in the data listings (e.g. 'L' or 'H').

14.2.1 Analysis for the Open-label Safety Analysis set

Clinical laboratory tests are performed at Screening, Baseline and Week 12 visits during the open-label period. Clinical laboratory values for hematology, chemistry and urinalysis (specific gravity and pH) will be summarized using descriptive statistics at Baseline and Week 12 visits. The change from Baseline values will also be summarized at the Week 12 visit.

The overall minimum and maximum post-baseline observed and change from Baseline values during the open-label period will also be summarized. For hemoglobin, hematocrit and uric acid, the above summaries will be presented for each gender as well as for both genders combined. For urinalysis with categorical results, the number and percentage of subjects will be tabulated by category at Baseline and Week 12 visit, and the denominator is the number of subjects with non-missing values for the given parameter and visit.

Laboratory values (except the ones that were only assessed at screening) will also be summarized in shift tables, to determine the number and percentage of subjects with values classified as below (low), within (normal), and above (high) normal ranges at Week 12 visit, overall post-baseline minimum and overall post-baseline maximum during the open-label period. For the Week 12 visit shift summary, the denominator is the number of subjects with non-missing values at Baseline and Week 12 visit for the given parameter. For the shift to the overall post-baseline minimum or maximum, the denominator is the number of subjects with non-missing baseline and at least 1 post-baseline value during the open-label period for the given parameter. For hemoglobin, hematocrit and uric acid, the shift summaries will be presented for each gender as well as for both genders combined.

The number and percentage of subjects with potentially clinically important (PCI) laboratory values at Week 12 visit and overall post-baseline during the open-label period will be summarized for selected parameters. PCI criteria for hematology and chemistry are listed in [Table 5](#) and PCI criteria for urinalysis are listed in [Table 6](#). For the overall post-baseline summaries of PCI values, all post-baseline values during the open-label period will be considered, including unscheduled and out of window values. Subjects with multiple PCI

values for a given parameter will be counted only once for that parameter. For the by-visit summary, the numerator for the percentage is the number of subjects with a post-baseline PCI value for the given parameter and visit, and the denominator is the number of subjects with non-missing values for the given parameter and visit. For the overall post-baseline summary, the numerator for the percentage is the number of subjects with at least 1 post-baseline PCI laboratory value during the open-label period for the given parameter, and the denominator is the number of subjects with at least 1 post-baseline laboratory value during the open-label period for the given parameter. For hemoglobin, hematocrit and uric acid, the count and percentage of subjects with PCI values will be presented for each sex as well as for both sexes combined. Subjects with any post-baseline PCI values will be presented in an additional listing.

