If the mean QTcF value from the set of ECGs done at Screening is prolonged due to an identifiable cause, and it is medically appropriate to address that cause, a repeat set of triplicate ECGs may be performed during Screening at the discretion of the Medical Monitor.

15. Has a heart rate <50 beats per minute. If bradycardia is secondary to iatrogenic or treatable causes and these causes are addressed, a heart rate assessment can be repeated during the screening period.
16. Has a significant unstable medical condition that could interfere with subject's ability to complete the study or comply with study procedures
17. Has severe renal impairment, severe or medically significant impairment of hepatic function, and/or a clinically significant laboratory abnormality that in the judgment of the Investigator or Medical Monitor will interfere with the conduct or interpretation of safety or efficacy evaluations in the study
18. Has one of the following screening laboratory results:
 - a. Platelets \leq 75,000/mm³
 - b. Hemoglobin \leq 9.5 g/dL if male, or \leq 8.5 g/dL if female
 - c. Neutrophils, absolute \leq 1000/mm³
 - d. Aspartate aminotransferase (AST) >2 \times upper limit of normal
 - e. Alanine aminotransferase (ALT) >2 \times upper limit of normal
 - f. Creatinine \geq 2 mg/dL
 - g. Hemoglobin A1c (HbA1c) \geq 8.5%
 - h. Abnormal free thyroxine (T4)
 - i. Vitamin B12 deficiency

Laboratory testing may be repeated during Screening at the discretion of the Medical Monitor.

19. Has a history of a positive test result for HIV or hepatitis C

20. Has a clinically significant CNS abnormality that is most likely contributing to the dementia or findings on MRI or CT including:
 - a. intracranial mass lesion (including but not limited to meningioma [$>1 \text{ cm}^3$ with evidence of peritumoral edema] or glioma)
 - b. vascular malformation
 - c. intracranial aneurysm >4 points by PHASES score ([Appendix L](#))
 - d. evidence of >4 hemosiderin deposits (definite microhemorrhage or superficial siderosis)
21. Requires treatment with a medication or other substance that is prohibited by the protocol
22. Has a body mass index (BMI) $<18.5 \text{ kg/m}^2$ or known unintentional weight loss $\geq 7\%$ of body weight over past 6 months

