14.2.2 Analysis for the Double-blind Safety Analysis Set

In addition to the open-label assessments at Screening, Baseline, and Week 12 visits, clinical laboratory tests are performed at Weeks 18, 26, and 38 visits during the double-blind period. Summaries for hematology, chemistry and urinalysis for the Double-Blind Safety Analysis Set will be similar to those described above for the Open-Label Safety Analysis Set and will include the following:

- Observed values and change from open-label baseline by visit including both open-label and double-blind visits; overall minimum and maximum for the open-label period; overall minimum and maximum for the double-blind period.
- Observed values and change from double-blind baseline by visit for the double-blind period; overall minimum and maximum for the double-blind period.
- Shifts from open-label baseline by visit including both open-label and double-blind visits; overall minimum and maximum for the open-label period; overall minimum and maximum for the double-blind period.
- Shifts from double-blind baseline by visit for the double-blind period; overall minimum and maximum for the double-blind period.

- Incidence of PCI values by visit including both open-label and double-blind visits; open-label overall post-baseline; double-blind overall post-baseline, based on the OL baseline.
- Incidence of PCI values by visit for the double-blind period; double-blind overall post-baseline, based on the DB baseline.

Urinalysis tests with categorical results will be summarized (number and percent of subjects in each category) by visit including both open-label and double-blind visits.

Table 5 Criteria for PCI Laboratory Values – Hematology and Chemistry

Analyte	Conventional Unit	Low PCI Criteria	High PCI Criteria	SI Unit	Low PCI Criteria	High PCI Criteria
Hematology (whole blood)						
Hemoglobin (male)	g/dL	<11	>18	g/L	<110	>180
Hemoglobin (female)	g/dL	<10	>17	g/L	<100	>170
Hematocrit (male)	%	<30	>55	L/L	<0.3	>0.55
Hematocrit (female)	%	<30	>50	L/L	<0.3	>0.5
Leukocyte (WBC Count)	x 10 ³ /uL	≤2.8	≥15	x 10 ⁹ /L	≤2.8	≥15
Neutrophils	x 10 ³ /uL	≤1.5	No upper limit	x 10 ⁹ /L	≤1.5	No upper limit
Platelet Count	x 10 ³ /uL	≤75	≥700	10 ⁹ /L	≤75	≥700
Chemistry (serum or plasma)						
ALT (SGPT)	U/L	No lower limit	≥3 X ULN	U/L	No lower limit	≥3 X ULN
AST (SGOT)	U/L	No lower limit	≥3 X ULN	U/L	No lower limit	≥3 X ULN
Total Bilirubin	mg/dL	No lower limit	≥1.5 ULN	umol/L	No lower limit	≥1.5 ULN

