14.4 Electrocardiogram

14.4.1 Analysis for the Open-label Safety Analysis Set

All ECGs will be centrally read; the interpretation by the central cardiologist is considered the official interpretation. 12-lead electrocardiogram (ECG) assessments are performed at Screening, Baseline, Weeks 2 and 12 during the open-label period.

ECG results (ventricular rate, PR, QRS, QT, and QTcF intervals) will be summarized using descriptive statistics at Baseline, Weeks 2 and 12 during the open-label period. The change from Baseline values will also be summarized at the Weeks 2 and 12.

QTcF (msec) observed and change from Baseline values during the open-label period will also be classified into the following categories:

- Observed: ≤450, 451 to 480, 481 to 500, and >500
- Change from Baseline: ≤10, 11 to 30, 31 to 60, and >60

The number and percentage of subjects in each category will be summarized at each visit and for the overall post-baseline maximum during the open-label period.

Electrocardiogram variable values will be considered PCI if they meet or exceed the upper limit values listed in [Table 8](#). The number and percentage of subjects with PCI ECG values at Weeks 2 and 12, and overall post-baseline maximum during the open-label period will be

summarized for selected parameters. For the by-visit summary, the numerator for the percentage is the number of subjects with a post-baseline PCI ECG value during the open-label period for the given parameter and visit, and the denominator is the number of subjects with non-missing values during the open-label period for the given parameter and visit. For the overall post-Baseline summary, the numerator for the percentage is the number of subjects with at least 1 post-baseline PCI ECG value during the open-label period for the given parameter, and the denominator is the number of subjects with at least 1 post-baseline ECG value during the open-label period for the given parameter. Subjects with any post-baseline PCI values will be presented in an additional listing.

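### For PCI criteria set by an observed value alone and not ruled out at entry, the laboratory and ECG incidence counts subjects who already met the criterion at Baseline

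*SAP*

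**What the plan says.** **Open-label laboratory data (SAP 14.2.1).** The overall post-baseline percentage has as its numerator "the number of subjects with at least 1 post-baseline PCI laboratory value during the open-label period for the given parameter". Baseline status plays no part there. Nor does it in the other half of the fraction: "the denominator is the number of subjects with at least 1 post-baseline laboratory value during the open-label period for the given parameter". Tables 5 and 6 define PCI by absolute limits or multiples of the upper limit of normal (ULN). They contain no Baseline term.

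**Open-label ECG (SAP 14.4.1).** The construction is the same: "the numerator for the percentage is the number of subjects with at least 1 post-baseline PCI ECG value". Subjects already PCI at Baseline stay in below the line too: "the denominator is the number of subjects with at least 1 post-baseline ECG value during the open-label period for the given parameter". The rule that sends the reader to the limits is "Electrocardiogram variable values will be considered PCI if they meet or exceed the upper limit values listed in". The table it points to is Table 8, which covers QRS, PR, QTcF and, as a separate row, change in QTcF.

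**Double-blind set (SAP 14.2.2 and 14.4.2).** Both sections call these counts incidence and include open-label visits. The laboratory section plans one summary tied to the open-label Baseline and another described as "Incidence of PCI values by visit for the double-blind period; double-blind overall post-baseline, based on the DB baseline". It does not say what being based on a Baseline does to the count. The ECG bullets carry no such phrase.

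**What the counts are meant to serve.** The safety endpoint (Protocol 2.4.1, SAP 2.4.1) concerns potentially clinically important *changes*. Protocol 9.5.4 likewise commits to the incidence of clinically significant *changes* in selected laboratory parameters. For vital signs, SAP 14.3.1 and Table 7 require a change from Baseline: together with an observed limit for blood pressure and pulse, and alone for weight.

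**The concern.** A subject who enters with mild anemia or a wide QRS and stays exactly the same counts as a PCI case. That is not a change, and it is not incidence in the usual sense of new cases among those at risk.

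The open-label period has most to lose, because no control arm shows what the percentage would have been without drug. PCI status at Baseline is not tabulated either: the by-visit counts are limited to post-baseline values. A reader of the PCI table alone cannot tell a stable pre-existing abnormality from one that arose on treatment.

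The plan is also uneven. It anchors vital-sign PCI to Baseline but leaves laboratory, QRS and PR criteria unanchored.

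**Working it through.** The documents state no PCI rate, so there is no figure to reproduce. Two checks apply.

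**1. Can a subject enter already meeting the criterion?** Entry limits are from Protocol 4.3 and PCI limits from SAP Tables 5, 6 and 8.

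| Criterion | Entry limit | PCI limit | PCI possible at entry? |
|---|---|---|---|
| Hemoglobin, men | excluded at 9.5 g/dL or below | below 11 g/dL | Yes: above 9.5 and below 11 |
| Hemoglobin, women | excluded at 8.5 g/dL or below | below 10 g/dL | Yes: above 8.5 and below 10 |
| Neutrophils | excluded at 1000/mm³ or below | 1.5 × 10³/µL or below | Yes: above 1.0 and up to 1.5 |
| QRS | 120 ms or more admitted, with its own QTcF ceiling | 120 ms or more | Yes |
| PR | no numeric limit | 220 ms or more | Yes |
| BUN, triglycerides, urinalysis items | no numeric limit | 30.0 mg/dL or more; above 300 mg/dL; Table 6 | Yes, subject to the judgment-based exclusion 17 |
| Creatinine | excluded at 2 mg/dL or more | above 1.5 × ULN | Only if ULN is below 2/1.5 = 1.33 mg/dL (ULN not given) |
| Platelets, low | excluded at 75,000/mm³ or below | 75 × 10³/µL or below | No, at Screening |
| ALT, AST | excluded above 2 × ULN | 3 × ULN or more | No, at Screening |
| QTcF | excluded above 470 ms at most | above 500 ms | No |
| QTcF change | none | above 60 ms | Already relative to Baseline |

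The laboratory exclusions apply to screening results. A PCI platelet or transaminase value at Visit 2 is therefore possible, but entry does not admit it by design.

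**2. How far can the reported rate sit from the new-onset rate?** Let b be the share PCI at Baseline, s the share of those still PCI afterwards, and r the new-onset rate among the rest. Under the SAP rule

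reported rate = b·s + (1 − b)·r.

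Restricted to subjects not PCI at Baseline, the rate is r. All values of b, s and r below are assumptions. With r = 3%:

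- b = 2%, s = 0.7: 0.014 + 0.98 × 0.03 = 4.3%
- b = 2%, s = 1.0: 0.020 + 0.0294 = 4.9%
- b = 20%, s = 0.7: 0.140 + 0.80 × 0.03 = 16.4%
- b = 20%, s = 1.0: 0.200 + 0.024 = 22.4%

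The share of counted subjects who were PCI before dosing runs from 0.014/0.0434 = 32% to 0.200/0.224 = 89%.

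**Double-blind period.** Assume b and s are equal in both arms, s = 1, and new-onset rates are 5% and 2%. The true ratio is 2.5 and the true difference 3 points. The reported difference is (1 − b) × 3 points.

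- b = 2%: 6.9% vs 3.96%; ratio 1.74, difference 2.9 points
- b = 10%: 14.5% vs 11.8%; ratio 1.23, difference 2.7 points
- b = 20%: 24.0% vs 21.6%; ratio 1.11, difference 2.4 points

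**The case against.** Several stronger readings are tempting, and the documents do not support them.

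- **That all laboratory and ECG PCI rates are affected.** They are not. QT prolongation is the ECG risk that Protocol 1.3.1 singles out, and both QTcF criteria are protected, one by the entry ceiling and the other by its definition. ALT/AST and low platelets are ruled out at Screening.
- **That the SAP presents these percentages as drug effects.** It does not. Section 14.2.1 speaks of number and percentage; incidence is the wording of 14.2.2 and 14.4.2. The summaries are descriptive, with no test or attribution.
- **That the two laboratory summaries in 14.2.2 are duplicates at double-blind visits.** They would agree if the Baseline reference does nothing. The phrase could equally mean that Baseline status is applied, and the SAP's Introduction places table specifications in a separate document. What can be shown is an undefined phrase.
- **That the randomized comparison is biased.** Baseline PCI balances in expectation, the risk difference barely moves, and the SAP plans no ratio.

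The plan also has other outputs anchored to Baseline: laboratory shift tables, change-from-Baseline summaries including PR and QRS, shifts in overall ECG interpretation, categorical urinalysis at Baseline and Week 12, and listings of subjects with PCI values. These help a reader see pre-existing abnormality. They do not give a new-onset PCI rate: laboratory shifts use normal ranges rather than PCI limits, and ECG shifts use the overall interpretation rather than PR or QRS.

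The objection therefore narrows the scope and the stakes. It does not remove the mismatch for the remaining criteria.

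**Conclusion.** The point holds for observed-value criteria that entry does not rule out: hemoglobin, neutrophils, BUN, triglycerides, urinalysis items, QRS and PR are examples. For these, the reported incidence mixes pre-existing with new abnormalities. It departs from the protocol's commitment to report changes and from the SAP's own vital-sign rule.

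The consequence is mainly open-label. Its size cannot be derived from the documents; the range of about 4% to 22% against a new-onset rate of 3% rests wholly on assumed inputs. For 14.2.2 the conclusion also depends on what the Baseline references mean. This is a minor matter of safety presentation that leaves the primary and key secondary analyses untouched, but it is cheap to put right.

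**What to change.** - For these criteria, report PCI incidence among subjects with a non-missing Baseline value that does not meet the same criterion. Apply the restriction to numerator and denominator, using the open-label or double-blind Baseline as applicable.
- State in 14.2.2 that this is what the two Baseline references mean, and apply the same rule in 14.4.2.
- Keep the all-subject count as a second line.

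The change uses data already collected and should be written into the SAP and table specifications before unblinding. It has two costs. Denominators become somewhat smaller. Subjects who were PCI at Baseline and then worsened (for example, a man whose hemoglobin falls from 10.5 to 8 g/dL) drop out of the new-onset line and appear only in the second line and the listings, which is why the second line should stay.

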14.2.2 Analysis for the Double-blind Safety Analysis Set

In addition to the open-label assessments at Screening, Baseline, and Week 12 visits, clinical laboratory tests are performed at Weeks 18, 26, and 38 visits during the double-blind period. Summaries for hematology, chemistry and urinalysis for the Double-Blind Safety Analysis Set will be similar to those described above for the Open-Label Safety Analysis Set and will include the following:

- Observed values and change from open-label baseline by visit including both open-label and double-blind visits; overall minimum and maximum for the open-label period; overall minimum and maximum for the double-blind period.
- Observed values and change from double-blind baseline by visit for the double-blind period; overall minimum and maximum for the double-blind period.
- Shifts from open-label baseline by visit including both open-label and double-blind visits; overall minimum and maximum for the open-label period; overall minimum and maximum for the double-blind period.
- Shifts from double-blind baseline by visit for the double-blind period; overall minimum and maximum for the double-blind period.

- Incidence of PCI values by visit including both open-label and double-blind visits; open-label overall post-baseline; double-blind overall post-baseline, based on the OL baseline.
- Incidence of PCI values by visit for the double-blind period; double-blind overall post-baseline, based on the DB baseline.

Urinalysis tests with categorical results will be summarized (number and percent of subjects in each category) by visit including both open-label and double-blind visits.

Table 5 Criteria for PCI Laboratory Values – Hematology and Chemistry

Analyte	Conventional Unit	Low PCI Criteria	High PCI Criteria	SI Unit	Low PCI Criteria	High PCI Criteria
Hematology (whole blood)						
Hemoglobin (male)	g/dL	<11	>18	g/L	<110	>180
Hemoglobin (female)	g/dL	<10	>17	g/L	<100	>170
Hematocrit (male)	%	<30	>55	L/L	<0.3	>0.55
Hematocrit (female)	%	<30	>50	L/L	<0.3	>0.5
Leukocyte (WBC Count)	x 10 ³ /uL	≤2.8	≥15	x 10 ⁹ /L	≤2.8	≥15
Neutrophils	x 10 ³ /uL	≤1.5	No upper limit	x 10 ⁹ /L	≤1.5	No upper limit
Platelet Count	x 10 ³ /uL	≤75	≥700	10 ⁹ /L	≤75	≥700
Chemistry (serum or plasma)						
ALT (SGPT)	U/L	No lower limit	≥3 X ULN	U/L	No lower limit	≥3 X ULN
AST (SGOT)	U/L	No lower limit	≥3 X ULN	U/L	No lower limit	≥3 X ULN
Total Bilirubin	mg/dL	No lower limit	≥1.5 ULN	umol/L	No lower limit	≥1.5 ULN
BUN	mg/dL	No lower limit	≥30.0	mmol/L	No lower limit	≥10.71
Creatine Kinase (CK)	U/L	No lower limit	≥3 ULN	U/L	No lower limit	≥3 ULN
Sodium	mEq/L	≤125	≥155	mmol/L	≤125	≥155
Potassium	mEq/L	≤3.0	≥5.5	mmol/L	≤3.0	≥5.5
Calcium, total	mg/dL	<8.0	>11.0	mmol/L	<2.0	>2.75
LDH	U/L	No lower limit	≥3 X ULN	U/L	No lower limit	≥3 X ULN
Alkaline Phosphatase	U/L	No lower limit	≥3 X ULN	U/L	No lower limit	≥3 X ULN
Uric acid (male)	mg/dL	No lower limit	≥10.5	umol/L	No lower limit	≥624.75
Uric acid (female)	mg/dL	No lower limit	≥8.5	umol/L	No lower limit	≥505.75
Albumin	g/dL	≤2.6	≥6.0	g/L	≤26	≥60
Total Protein	g/dL	≤5.0	≥10.0	g/L	≤50	≥100
Chloride	mEq/L	≤85	≥120	mmol/L	≤85	≥120
Glucose (random)	mg/dL	≤45.1	≥200.0	mmol/L	≤2.48	≥11
Serum Creatinine	mg/dL	NA	>1.5 ULN	umol/L	NA	>1.5 ULN
Triglycerides	mg/dL	NA	>300	mmol/L	NA	>3.39
GGT	U/L	NA	≥3 ULN	U/L	NA	≥3 ULN

NA = not applicable

Table 6 Criteria for PCI Laboratory Values - Urinalysis

Urinalysis (qualitative dipstick)	Low PCI Criteria	High PCI Criteria
Blood (occult blood)	Not Applicable	≥ Moderate
Protein	Not Applicable	≥ 100 mg/dL
Glucose	Not Applicable	≥ 500 mg/dL

The pregnancy results (positive or negative) for female subjects will be presented in a listing.

